Targeted recruitment outreach of all eligible potential participants will be conducted through phone calls, mailings, and emails as well as in-person outreach for UM patients at routine endocrinology appointments and in-person recruitment at fairs, camps and/or community events for any eligible youth with T1D. Electronic advertisements will also be posted on UMHealthResearch.org and clinic website umpedsdiabetes.com. The study team will inform the staff and providers within Pediatric Endocrinology of the study and its requirements and request referrals. Paper advertisements will be distributed in Pediatric Endocrinology clinic rooms at C.S. Mott Children's Hospital and e-newsletter. The team has extensive experience utilizing hospital electronic medical records to screen participants for eligibility.

In addition, the team will utilize listservs and other points of contact (e.g. Facebook groups) of T1D-focused groups in Southeast Michigan. For example, after gaining permission from colleagues at the local chapter of the Juvenile Diabetes Research Foundation (JDRF), the approved study email, flyer, text, and/or umhealthresearch.org link could be sent to members of their listserv or posted to their Facebook group. Project clinicians will also work with outside endocrinologists to have them share the study with their patients. If interested, patients will initiate contact with the study team since the investigators will not have access to other clinic's patient names, addresses or phone numbers. Current families enrolled in the study will also be able to share the study with their T1D network or community via word-of-mouth or by sharing approved recruitment materials; anyone interested would then initiate contact with the study team.

Interested families will complete eligibility screening through an intake call or in person, based on their preferred method. During the intake, informed consent/assent, study activities and random assignment will be detailed. Participants will be randomly assigned to intervention group at enrollment using a random number generator. We will employ a block randomization scheme stratified for youth sex and age (+/- 1 year), to ensure equal allocation to control and intervention groups.

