**Procedures.** The adolescent and their parent will be scheduled to visit our research offices at the Center for Human Growth and Development (CHGD), which are set up for family-friendly visits. A parking pass will be provided. Pre-test and post-test assessments will be completed at CHGD (see **Intervention and Attention Control Protocols**). The pre-test visit will consist of completing SR behavioral assessments (youth) and questionnaires (youth and parent), medication adherence questionnaires (youth and parent), and introduction of intervention (for the intervention group) or control activities (for the control group; youth and parent). We will also show youth and parents the umpedsdiabetes.com website as a source of information on medication adherence, stress relief, and managing medications.

We will provide all parents with contact information for resources for themselves and their adolescent in the community to access mental health care, as well as social services and resources as needed. During the consenting process we will highlight the referral resource list, noting that it includes referrals for a range of services that families might find useful, including community-based behavioral health resources for parents and children. If a parent specifically requests assistance with finding an appropriate referral, PI [name] or Co-I [name] will contact the parent to identify an appropriate referral based on individual concerns.

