We have balanced feasibility with rigorous measurement; the Pre-test visit is anticipated to take up to two and a half hours to complete all study activities. The post-test visit will be nearly identical to the pre-test with the exception of the intervention or control activities, and is anticipated to take 1.5 hours. Participants can complete post-test surveys remotely by receiving links to the surveys stored in the project's secure electronic database (REDCap). Patient diabetes devices (glucometer, insulin pump, and/or continuous glucose monitor (CGM)) will be downloaded at pre-test and post-test visits in adjacent clinic space to obtain these clinical data as a measure of adherence. For the post-test visit, devices may also be downloaded remotely and securely. The family will be escorted to co-located UM-lab sites or instructed to visit any UM-lab site on their own within 7 days of pre-test to have blood drawn to assess for HbA1c. A review of the electronic medical record will be conducted after the family has completed the post-test to assess number and purpose of clinic visits and any health events (e.g., DKA). We will inform the families that we may look at the teen's medical record up to 1 year after the 2nd study visit in order to review T1D health events. Youth will be offered up to \$175 and parents up to \$100 using a pro-rated incentive structure designed to enhance retention. For completing their home practice, youth in the intervention group will offered up to \$80 more and will be entered into a lottery to win a gift card.

**Measures.** We will use multi-method assessment. Post-test assessments will be conducted 8-10 weeks after pre-test, based on anticipated changes in self-regulation, medication adherence, and HbA1c across this period of time, and the optimal timing of intervention delivery as determined during the UH2 phase. Table 6 outlines self-regulation assessments; Table 7 outlines medical regimen adherence and T1D assessments.

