**Self-regulation.** SR will be assessed using the multi-method assays developed in our UH2 study. Adolescents in the UH3 phase will complete SOBC Network-developed measures that are hypothesized to change as a result of our intervention but that we were not able to use in the UH2 due to the younger age of our sample (e.g., CFC; 5-trial Delay Discounting). All assays were shown to be psychometrically reliable in our own and/or other SOBC Network work, or with adolescents in prior research. EF will be assessed using objective tasks and parent-reports to evaluate working memory (Backward Digit Span; BRIEF); inhibitory control (Go-no-go task; BRIEF); organization/planning (BRIEF). Parents will also complete a digit span and Go-no-go task to assess EF. ER will be assessed using youth self-report and parent-report to evaluate affect dysregulation (SIDES) and perceived stress (NIH PSS) and youth self-report of anxiety (GAD-7) and positive and negative affect (PANAS). FO will be assessed using youth self-report and objective tasks to evaluate self-efficacy (NIH Self-Efficacy), consideration of future consequences of actions (CFC); and delay discounting (5-trial task). We also seek to identify potential mechanisms of association between parent SR capacity and youth T1D outcomes, including diabetes-relevant family processes that have been identified as important in shaping health outcomes for youth with T1D (Table 8).

| Table 6   | Specific Construct   | Measure Details                                | Who / Data Source                               |
|---|--|--|---|
| Intake  |  |  |   |
|   | Regimen (Parent and Child), Parent
Depression, Family Chaos, Family
Composition and Income, Demographics | 29 min   | Parent for all;
Child self-report on Regimen |
| Executive Function  |  |  |   |
| Forward & Backwards
Digit span   | Working memory   | 7 min (online)                                 | Parent and child complete task                  |
| Go No Go task   | Inhibitory control   | 7 min (online)                                 | Parent and child each complete task             |
| Behavior Rating
Inventory of Executive
Function – A                     | EF broad   | 15 min (75 items)                              | Parent self-report                              |

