#### **Intervention and Attention Control Protocols**

All youth in the intervention condition will receive the bundled intervention, which focuses on EF, ER, and FO. The intervention will occur mostly through home practice and be supplemented by engaging youth remotely using approaches that PI [name] has used in her work with teens managing chronic illness and in other studies with this population (e.g., text based reminders and mobile apps to practice techniques). Intervention activities will be introduced after evaluation activities are completed for the pre-test and we will monitor home practice to assess dosage as in the UH2 phase (e.g., number of NBack sessions; relaxation practice; EFT cues played).

- 1. EF Intervention. We will use the NBack intervention as in the UH2 phase. Youth will be shown how to play a game wherein they recall which image they saw in prior sequences. As in the UH2, participants will be given a tablet with the game loaded on it to play at home.
- 2. ER Intervention. In the UH2 phase, participants learned how to engage in relaxation and biofeedback activities during in person visits by completing activities (e.g., modulating breathing to keep heart rate and skin conductance within a certain range) on a computer while wearing sensors. They were told to complete the relaxation activities on their own at home, but were not given access to a computer-based version to practice. In the UH3, we will conduct similar in-person relaxation and biofeedback training but also show participants how to practice these activities at home using commercially available apps that PI [name] uses clinically (e.g., Heartmath and Insight Timer). These will be loaded onto the tablets with the Nback task and/or onto the participant's smartphone.

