Youth will be randomly assigned to receive intervention or control using a random number assignment protocol we used in the UH2 phase. To test whether the interventions were effective in changing self-regulation targets (Aim 1), medical regimen adherence and T1D health outcomes (Aim 2), and diabetes relevant family processes (on an exploratory basis), we will use an intent-to-treat analysis (all analyses will use an alpha value of p<.05). Baseline comparability of the groups will be assessed for multiple variables using t-tests for continuous variables (e.g., home chaos) and  $\chi^2$  tests for categorical variables (e.g., regimen type). We will use generalized linear (for continuous adherence and health outcomes) and logistic regression (for dichotomous adherent/nonadherent outcomes) to compare changes in SR, adherence and health outcomes across the two groups (treatment vs. control;  $\alpha = 0.05$ ). We anticipate that some children will have only partial adherence to the intervention (i.e. attend a subset of sessions), thus we will conduct a dose-response analysis where dose corresponds to number of sessions, controlling for covariates that relate to number of sessions attended and outcome of interest. Sex will be examined as a biological variable as some differences have been identified in SR-adherence associations. **Power.** In UH3 we will test the feasibility of assaying SR in a new sample and detecting change in SR targets and medication adherence. We anticipate medium effect sizes of 0.6 with the bundled interventions, so our proposed sample size of 94 (47 per group) should result in sufficient statistical Power of 82% to detect such effects using a two-sided Type I error alpha of 0.05. In addition, controlling for baseline variables that relate to outcome would reduce the residual variance and further increase the statistical Power.

**UH3 Study Timeline.** Table 9 outlines the timeline for UH3 activities. We include 3 months of "start-up" to refine assays and interventions (which are largely the same as in the UH2 phase), obtain IRB approval, and train staff. We will enroll 2 new participants per week to reach our recruitment goals (n=94), which is feasible.

The rhythm of data collection in prior studies is similar to that proposed here, and we are thus confident in the feasibility of the project. Co-I [name]'s successful recruitment in the UM Diabetes clinics she runs

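### The arm is assigned at enrolment, before the pre-test tasks and questionnaires, and nothing in the plan withholds it until they are complete

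*Combined protocol and SAP*

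**What the plan says.** In the Recruitment part of the Approach section, families are screened by an intake call or in person: "During the intake, informed consent/assent, study activities and random assignment will be detailed". The same paragraph continues: "Participants will be randomly assigned to intervention group at enrollment using a random number generator". Randomisation is blocked and stratified by sex and age.

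Procedures then describes a separate appointment: "The adolescent and their parent will be scheduled to visit our research offices". Baseline outcomes are collected there: "The pre-test visit will consist of completing SR behavioral assessments (youth) and questionnaires (youth and parent), medication adherence questionnaires (youth and parent"). Diabetes devices are downloaded at the same visit. Blood for HbA1c may be drawn at a co-located laboratory, or the family may be "instructed to visit any UM-lab site on their own within 7 days of pre-test".

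The section on the intervention and attention control protocols fixes the order within that visit: "Intervention activities will be introduced after evaluation activities are completed for the pre-test".

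The Statistical Analysis Plan uses intent-to-treat and will "compare changes in SR, adherence and health outcomes across the two groups". Neither the protocol nor the SAP text describes allocation concealment, masked pre-test assessors, or holding the arm back from families until baseline is complete.

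**The concern.** The arm is not needed until the pre-test evaluation ends and the intervention is introduced. Assigning it sooner brings no stated benefit, since the two stratification factors are equally available after the pre-test. It opens two risks.

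1. **Baseline reporting.** The self-regulation measures in Table 6 are youth or parent reports and effort-dependent tasks. The self-care inventory in Table 7 is youth and parent report, and bolus counts for youth on injections are self-reported. The arms also give families different reasons to engage: intervention youth can earn up to $80 more and enter a lottery, while controls receive existing care. If the arm is known when these measures are taken, the answers or effort may differ by arm. Because the analysis compares changes, a distorted baseline enters the treatment estimate. It could create an apparent effect or hide a real one, depending on its direction.
2. **Loss before pre-test.** If enrolment is at intake, a family can be randomised and never attend. It then belongs to the intent-to-treat population without pre-test outcomes. The SAP offers general multiple imputation and sensitivity analyses, but no specific rule for such families.

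**Working it through.** **The plan's own figure.** The SAP gives 82% power for 47 per group, standardised effect 0.6 and two-sided alpha 0.05. By normal approximation the standard error is √(2/47) = 0.206, the noncentrality is 0.6/0.206 = 2.91, and power is Φ(2.91 − 1.96) = 82.9%. The two-sample t-test gives 82.1%. The figure reproduces, and it assumes that all 94 are analysed.

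**Sequence.** The steps read: intake and enrolment with assignment; a scheduled pre-test visit; assessments; introduction of arm activities. If enrolment instead takes place at the start of the pre-test visit, assignment still comes before the assessments. Only the risk of loss before the visit depends on which reading is right.

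**Illustration of the reporting risk.** The documents give neither the shift *b* nor the pre-post correlation *r*; both are assumptions. Outcomes have SD 1, there is no true effect, and n = 47 per arm.

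- Change score: bias = *b*; standard error = √(2(1 − *r*)) × √(2/47).
- Baseline-adjusted: bias = *r* × *b* in absolute value; standard error = √(1 − *r*²) × √(2/47).
- Rejection rate with δ = bias/standard error: 1 − Φ(1.96 − δ) + Φ(−1.96 − δ).

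At *b* = 0.2 and *r* = 0.5:

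- Change score: δ = 0.2/(1 × 0.206) = 0.97, so the rate is about 16%.
- Adjusted: δ = 0.1/(0.866 × 0.206) = 0.56, so the rate is about 9%.

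False-positive rates when the shift is present at baseline only:

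| *b* (SD) | Change score, *r* = 0.3 / 0.5 / 0.7 | Adjusted, *r* = 0.3 / 0.5 / 0.7 |
|---|---|---|
| 0.1 | 7% / 8% / 10% | 5% / 6% / 8% |
| 0.2 | 13% / 16% / 24% | 6% / 9% / 16% |

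**How much depends on the shift disappearing.** Keep *b* = 0.2 and *r* = 0.5.

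- Same shift at both visits: the change-score bias is 0.2 − 0.2 = 0, so the rate is 5%. The adjusted bias is 0.2 − 0.5 × 0.2 = 0.1, so the rate is about 9%.
- Shift at post-test only: the change-score bias is 0.2, about 16%. The adjusted bias is 0.2, δ = 0.2/0.179 = 1.12, about 20%.

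A simulation of 20,000 null trials agrees. Change-score and adjusted rates were 16% and 8% (baseline only), 5% and 8% (both visits), and 15% and 19% (post-test only).

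**Illustration of the loss risk.** No loss rate is given. If 5% or 10% of randomised families left before pre-test and contributed no outcome data, the analysed number per arm would be 47 × 0.95 = 44.65 or 47 × 0.90 = 42.3. The t-test power would be 80.1% or 77.9%.

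**The case against.** The strongest reply is that assignment is not disclosure. The intake text says that the process of random assignment is explained; it does not say that the result is given. A reader might infer that families are told their arm before the pre-test, but no section says so. This stands, and it limits the point to what could happen under the plan as written.

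Enrolment is also never dated. Procedures mentions the consent process after describing the visit, which would leave little room for loss before pre-test. The intake battery in Table 6 points the other way. Both arms share the base payments of up to $175 for youth and $100 for parents, so control families also have reason to attend. The loss risk is therefore conditional.

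A reader might also infer that every change comparison is exposed, or that families could leave before any baseline exists. Neither is supported. Device data cover the prior two weeks, HbA1c reflects the prior 2-3 months, and health events come from chart review. Intake already supplies covariates, including "Child self-report on Regimen", and eligibility requires an HbA1c value. The option of an HbA1c draw up to 7 days after pre-test might look like a further flaw, but at most 7 days of a 2-3 month measure would follow the start of the intervention.

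Finally, high error rates can be produced only by assuming a reporting shift at baseline that has gone by post-test. Participants will know their arm at post-test under either sequence, so changing the order does not remove reporting bias altogether. That is correct.

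What these replies do not answer is the stated rule. The plan puts assignment before the assessments, and its statement on when intervention activities begin orders only the content, not when the arm is generated or revealed.

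**Conclusion.** The point holds as one about the timing of allocation. The plan assigns the arm before the pre-test assessments and contains no safeguard that keeps it unknown until they are complete. The exposure lies in youth and parent reports and effort-dependent tasks.

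The size cannot be determined from the documents. The 16% and 9% figures rest on an assumed 0.2 SD shift at baseline only and a pre-post correlation of 0.5; they show that the risk is not negligible and do not estimate it. The 82% power calculation is not in dispute, and the 80.1% and 77.9% figures depend on assumed loss rates. Assigning after baseline is standard practice and nearly free here, so the change is worth making even though the harm is unproven.

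**What to change.** Amend the assignment sentence under Recruitment along these lines: *The arm is assigned, or released to staff and family, only after all pre-test questionnaires, tasks and device downloads are complete, and immediately before the intervention or control activities are introduced.* The study already uses REDCap, which could hold the allocation until then. If the arm is already withheld in practice, the sentence simply documents it.

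The protocol's COVID-19 follow-up text shows that some participants have already finished post-test. The change should therefore apply to new participants, with its date recorded. The cost is one protocol sentence and a later opening of the allocation. Visits, staff, sample size and power calculation do not change. The small downside is two allocation timings within one sample, which the recorded date makes visible. The 7-day HbA1c window needs no change.

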#### **Intervention and Attention Control Protocols**

All youth in the intervention condition will receive the bundled intervention, which focuses on EF, ER, and FO. The intervention will occur mostly through home practice and be supplemented by engaging youth remotely using approaches that PI [name] has used in her work with teens managing chronic illness and in other studies with this population (e.g., text based reminders and mobile apps to practice techniques). Intervention activities will be introduced after evaluation activities are completed for the pre-test and we will monitor home practice to assess dosage as in the UH2 phase (e.g., number of NBack sessions; relaxation practice; EFT cues played).

- 1. EF Intervention. We will use the NBack intervention as in the UH2 phase. Youth will be shown how to play a game wherein they recall which image they saw in prior sequences. As in the UH2, participants will be given a tablet with the game loaded on it to play at home.
- 2. ER Intervention. In the UH2 phase, participants learned how to engage in relaxation and biofeedback activities during in person visits by completing activities (e.g., modulating breathing to keep heart rate and skin conductance within a certain range) on a computer while wearing sensors. They were told to complete the relaxation activities on their own at home, but were not given access to a computer-based version to practice. In the UH3, we will conduct similar in-person relaxation and biofeedback training but also show participants how to practice these activities at home using commercially available apps that PI [name] uses clinically (e.g., Heartmath and Insight Timer). These will be loaded onto the tablets with the Nback task and/or onto the participant's smartphone.
- 3. FO Intervention. In the UH2 phase, we developed an EFT intervention based on SOBC Network Member [name]'s work. The EFT intervention, in which participants generate positive upcoming events and describe these events using prompts to elicit concrete, episodic language, is hypothesized to promote future-oriented thinking because the participant is encouraged to mentally project and preexperience the future event in the present. Our EFT intervention showed positive impact on the number of episodic, descriptive words our UH2 child participants used when describing future events. For the UH3 phase, as we are working with adolescents who have greater cognitive capacity to engage in such activity, and who are at an age when developing FO is critical, As in our UH2 phase, participants will be asked to envision and describe future events they are looking forward to, using concrete, vivid descriptive language. The interventionist will transcribe the participant's descriptions, or cues, and concise prompts will be texted to participants at home. The participant will be prompted to look at the cues at home at specified times of day (e.g., 7am and 3:30PM).

Attention Control Protocol. Youth in the control condition will receive care that is already in place. After posttest data collection is complete participants will be asked if they would like to receive a summary of study findings at the completion of the study and if results are favorable, will have the option of learning intervention techniques.

Intervention and Attention Control Fidelity Measures. As in our UH2 phase, we will assess fidelity of delivery for both the intervention as well as the attention control condition by videotaping and coding a subset of sessions.

COVID-19 follow up study. In light of events with the COVID-19 pandemic, we are inviting participants who have finished the post-test visit to complete an online survey to help us understand how families are coping. All data collection will occur remotely. The follow up consists of 12 questionnaires that parents answered before (10 for teens) plus 1 new survey [11 items] about life changes during the COVID-19 pandemic. In addition, we will include the COVID-19 survey in our battery for all pre-test visits going forward.

In the COVID-19 follow-up, parents will be asked to answer the following 12 questionnaires again: Family Chaos, CESD, Difficulties in Emotion Regulation Scale, Perceived Stress (parent report on child), Self-Efficacy (parent report on child), SCI-R, T1D Regimen Survey, Perceived Stress (self-report), Revised Diabetes Family Conflict Scale, Problem Areas in Diabetes Parents of Teens (P-PAID-T), Diabetes Family Responsibility Questionnaire, PROMIS. In addition, parents will be asked the 11-item COVID Family Stress scale. The COVID-19 Family Stress scale measures increased stress for families in light of the pandemic. It consists of 11 items in areas such as child care, job loss, and physical health.

Teens will be asked to answer the following 10 questionnaires again: Perceived Stress (self-report), Affect Dysregulation scale, Self-Efficacy (Self-report), Consideration of Future Consequences, PANAS, GAD7, SCI-R, T1D Regimen Survey, Problem Areas in Diabetes – Teen (PAID-T), PROMIS. As well, teens will be asked to answer an 11-item version of the COVID Family Stress Scale modified for their age group.

Parent and teen participants who choose to participate in the COVID-19 follow up will receive an additional \$25 for completing the follow-up.

